1. LIST OF ABBREVIATIONS

Table 1: List of Abbreviations

Abbreviation	Term
AE	Adverse Event
BP	Blood Pressure
CADI	Cardiff Acne Disability Index
CRF	Case Report Form
CSR	Clinical Study Report
DRL	[name]
FDA	Food and Drug Administration
IGA	Investigator's Global Assessment
ITT	Intent-to-Treat Population
IWRS	Interactive Web-Based Response System
LOCF	Last Observation Carried Forward
MedDRA	Medical Dictionary for Regulatory Activities Terminology
n	Observed Sample Size
N	Total Sample Size
PCS	Potentially Clinically Significant
PP	Per-Protocol Population
PT	Preferred Term
SAE	Serious Adverse Event
SAS	Statistical Analysis System
SD	Standard Deviation
SOC	System Organ Class
TEAE	Treatment-Emergent Adverse Event
TEAESI	Treatment Emergent Adverse Event of Special Interest
TESAE	Treatment-Emergent Serious Adverse Event
TSR	Technical Summary Report
WHO	World Health Organization
WHODD	World Health Organization Drug Dictionary

2. INTRODUCTION

The purpose of this statistical analysis plan (SAP) is to describe the planned analyses and data displays to be included in the Clinical Study Report (CSR) for Protocol DFD-03-CD-008.

Protocol Revisio	n Chronology:	
Protocol	02-JUN-2017	Original
Amendment 01	02-JUN-2017 06-NOV-2017	Amendment No. 01: This protocol amendment was implemented based on recommendations from the FDA and includes the following: 1. To update Inclusion Criteria #3 to include subjects 9 to 11 years of age that will be enrolled at selected site(s) and to clarify that efforts will be made to include approximately 8 subjects in the 9-11 years age group in the 2 arms of DFD-03 lotion (active and vehicle included) where a treatment assignment schedule will be created with kit numbers randomly assigned to study products which is independent from the treatment assignment schedule created for ages 12 years and older. 2. To update Inclusion Criteria #5 to specify that at selected sites(s), subjects with acne lesions on the chest and/or back (including shoulders) in addition to those on the face will treat these affected areas and to specify that up to 12 subjects with acne involvement on the face, chest and/or back including shoulders will be randomized to treatment with either DFD-03 (tazarotene) Lotion 0.1%, Tazorac (tazarotene) Cream, 0.1%, Vehicle Lotion or Vehicle Cream in a ratio of 2:2:1:1. 3. To update Inclusion Criteria #6 to specify there is no required inflammatory lesion count for subjects 9-11 years of age. 4. To update Inclusion Criteria #7 to specify there is no required non-inflammatory lesion count for subjects 9-11 years of age. 5. To update Inclusion Criteria #9 to clarify that women who are surgically sterilized (e.g. hysterectomy, bilateral tubal ligation, bilateral oophorectomy) at least 1 year prior to baseline or have been postmenopausal for at least 1 year prior to baseline, do not have to practice birth control measures. 6. To clarify that if acne lesions are present on the chest and/or back (including shoulders), that these lesions will be counted and recorded separately at each visit from Baseline to Week 12 and local cutaneous tolerance evaluation will be assessed and recorded separately. 7. To clarify restriction on who may be involved with the dispensing or return of study medication. I

This SAP was developed in accordance with ICH E9 guideline. All decisions regarding final analysis, as defined in this SAP document, will be made prior to Database Freeze (unblinding) of the study data. Further information can be found in the protocol.

The statistical analysis plan (SAP) is based on:

- Protocol No. DFD-03-CD-008, Version 2.0, Amendment 01, dated 06-NOV-2017
- ICH guidelines E4 and E9 (Statistical Principles for Clinical Trials)
- Discussions with the FDA

The purpose of this document is to provide details on study populations and on how the variables will be derived, how missing data will be handled as well as details on statistical methods to be used to analyze the safety and efficacy data for Study Protocol No. DFD-03-CD-008.

The document may evolve over time, for example, to reflect the requirements of protocol amendments or regulatory requests. However, the final SAP must be finalized, approved by the Sponsor, and placed on file before database is locked. Deviations from the final approved plan will be noted in the clinical study report.

3. STUDY OBJECTIVES AND ENDPOINTS

3.1. Study Objectives

The objectives of this study were to determine the safety and local tolerability of DFD-03 (tazarotene) Lotion 0.1% and to compare it with Tazorac (tazarotene) 0.1% Cream in the topical treatment of acne vulgaris for 12 weeks.

3.2. Study Endpoints

3.2.1. Primary Endpoints

The primary safety endpoints are:

- Local Cutaneous Safety Evaluation Data (dryness, non-lesional erythema, peeling, stinging, burning, and itching). Reactions on the face were assessed separately from those on the chest/back/shoulders.
- Treatment-Emergent Adverse Events (TEAEs).

3.2.2. Secondary Endpoints

The secondary safety endpoints are:

- Vital Signs (blood pressure and pulse rate)
- Physical Examination Data

The secondary efficacy endpoints are:

- Proportion of Subjects with IGA Success at Weeks 4, 8 and 12. IGA success is defined as an IGA score of 0 (Clear) or 1 (Almost Clear) with at least a 2-grade reduction from baseline.
- Absolute Change from Baseline in Inflammatory Lesion Counts at Weeks 4, 8 and 12. The following location of lesions will be summarized separately: face and chest/back/shoulders.
- Absolute Change from Baseline in Non-Inflammatory Lesion Counts at Weeks 4, 8 and 12. The following location of lesions will be summarized separately: face and chest/back/shoulders.
- Percent Change from Baseline in Inflammatory Lesion Counts at Weeks 4, 8 and 12. The following location of lesions will be summarized separately: face and chest/back/shoulders.
- Percent Change from Baseline in Non-Inflammatory Lesion Counts at Weeks 4, 8 and 12. The following location of lesions will be summarized separately: face and chest/back/shoulders.
- Change from Baseline in Cardiff Acne Disability Index (CADI) at Weeks 4, 8 and 12. The following location of lesions will be summarized separately: face and chest/back/shoulders.

4. STUDY DESIGN

4.1. Summary of Study Design

This was a multicenter, randomized, double-blind, parallel-group, active-controlled study. Approximately 150 subjects with mild to moderate facial acne vulgaris were randomized in a 2:2:1:1 ratio to treatment with DFD-03 (tazarotene) Lotion 0.1%, Tazorac (tazarotene) Cream, 0.1%, Vehicle Lotion, or Vehicle Cream. During the 12-week treatment period subjects randomized to DFD-03 Lotion or Vehicle Lotion used the study drug twice daily with approximately 12 hours between applications. Subjects randomized to Tazorac Cream or Vehicle Cream used the study drug once daily in the evening.

At selected site(s), subjects with acne lesions of any severity on the chest and/or back (including shoulders) may have been enrolled provided they have met all inclusion criteria including mild to moderate acne on the face and have not met any exclusion criteria and treated all areas affected with acne on the face, chest and/or back, including shoulders, if applicable. Up to 12 subjects with acne involvement on the face, chest and/or back including shoulders were randomized to treatment with either DFD-03 (tazarotene) Lotion 0.1%, Tazorac (tazarotene) Cream, 0.1%, Vehicle Lotion or Vehicle Cream in a ratio of 2:2:1:1.

Also, there were selected site(s) that enrolled approximately 8 subjects who are 9 years of age to 11 years of age. They were randomized to DFD-03 group only in a 1:1 ratio of DFD-03 (tazarotene) Lotion 0.1% to Vehicle Lotion. The total number of approximately 150 subjects in the study included up to 12 subjects with acne on the chest and/or back, and approximately 8 subjects in the age group of 9-11 years.

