4.3. Sample Size Considerations

The sample size was not powered to obtain statistical significance, but was expected to provide an estimate on comparability of local tolerability/safety of DFD-03 versus Tazorac Cream and their respective Vehicles.

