4.4. Randomization

Subjects were assigned randomly to one of the four treatment arms, DFD-03 (tazarotene) Lotion 0.1%, Tazorac (tazarotene) Cream, 0.1%, Vehicle Lotion or Vehicle Cream in a 2:2:1:1 ratio (50 subjects each to DFD-03 Lotion and Tazorac Cream, and 25 subjects each to Vehicle Lotion and Vehicle Cream). A treatment assignment schedule was created with kit numbers randomly assigned to study products. The date and time of randomization and the bottle/tube number should have been entered on the eCRF.

[name], Ltd Statistical Analysis Plan, Version 2.0

For the selected site(s) enrolling subjects in the 9-11 age group, subjects were assigned randomly to one of the two treatment arms, DFD-03 (tazarotene) Lotion 0.1%, and 0.1%, Vehicle Lotion in a 1:1 ratio (4 subjects each to DFD-03 Lotion and Vehicle Lotion). A treatment assignment schedule was created with kit numbers randomly assigned to study products, which is independent from the treatment assignment schedule created for ages 12 and older.

For the selected site(s) enrolling subjects with acne involvement on the face, chest and/or back including shoulders, subjects were assigned randomly to treatment with either DFD-03 (tazarotene) Lotion 0.1%, Tazorac (tazarotene) Cream, 0.1%, Vehicle Lotion or Vehicle Cream in a 2:2:1:1 ratio. Since these subjects were treating their face, chest and/or back and shoulders, the subject kit size contained more study medication for application. A treatment assignment schedule was created for these larger kit sizes with kit numbers randomly assigned to study products, which is independent from the treatment assignment schedules created for ages 9-11 and 12 and older.

A unique subject number was assigned to each subject. The randomization number (kit number) was designated as the subject number. The subject maintained the same subject number and treatment assignment throughout the study. Subject numbers were assigned immediately prior to dispensing study medication and were assigned starting with the lowest available number at the study site.

The Investigator designated an independent third party study medication dispenser who dispensed to qualified subjects, collected all bottles/tubes of study product and dispensed and collected diaries.

No stratification based on age or other characteristics was performed.

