6.4. Data Presentation Conventions

Continuous variables (e.g. age) are summarized using descriptive statistics (the number of subjects with available data, the mean, standard deviation (SD), median and minimum and maximum). Categorical variables (e.g. race) are summarized using counts and percentages. Percentages are calculated using the total subjects per treatment group.

The following conventions are applied to all data presentations and summaries.

For continuous variables, all mean and median values are formatted to one more decimal place than the measured value. Standard deviation values are formatted to two more decimal places than the measured value. Minimum and maximum values are presented with the same number of decimal places as the measured value.

For categorical variables, the number and percentage of responses are presented in the form XX (XX.X %) where the percentage is in the parentheses.

Date variables are formatted as DDMMMYYYY for presentation. Time is formatted in military time as HH:MM for presentation.

Wherever possible, data will be decimal aligned.

P-values, if applicable, will be presented to 4 decimal places. If the p-value is less than 0.0001 then it will be presented as <0.0001.

Unless otherwise stated, any statistical tests performed will use 2-sided tests at the 5% significance level.

The table and listing shells and table of contents as part of this SAP provide the expected layout and titles of the tables, listings and figures. Any changes to format, layout, titles, numbering, or any other minor deviation will not necessitate a revision to the SAP nor will it be considered a deviation from planned analyses. Only true differences in the analysis methods or data handling will necessitate such documentation. The appropriate listings supporting the tables will be included and are not specified in the individual sections throughout the document.

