6.5.2. Safety Population

All subjects who receive at least one confirmed dose of study product and provide any post baseline safety information will be included in the safety population. No imputation will be made for missing safety data.

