7.3. Demographic and Baseline Characteristics

The following demographic and baseline characteristics will be summarized by treatment and overall:

- Age (Years)
- Age Group (12 16 Years, 17 64 Years, 65 Years or Older)
- Gender (Male, Female)
- Race (White, Black or African American, Asian, American Indian or Alaskan Native, Native Hawaiian or Other Pacific Islander and Other)
- Ethnicity (Hispanic or Latino, Non-Hispanic or Non-Latino)
- Fitzpatrick Classification Scale (I, II, III, IV, V, VI)
- Investigator's Global Assessment (IGA) at Baseline (0 = Clear, 1 = Almost Clear, 2 = Mild, 3 = Moderate, 4 = Severe)
- Inflammatory Lesion Count
- Non-inflammatory Lesion Count

Age will be computed using date of birth and baseline visit date with details in Section 6.7.1.

The Fitzpatrick skin scale classifies a person's complexion and tolerance of sunlight. It is commonly used by many practitioners to determine how someone will respond or react to facial treatments. The Fitzpatrick skin scale is presented in Table 4 below.

Table 4: Fitzpatrick Classification Scale

Skin Type	Skin Color	Characteristics
I	White; very fair; red or blond hair; blue eyes; freckles	Always burns, never tans
II	White; fair; red or blond hair; blue, hazel, or green eyes	Usually burns, tans with difficulty

Skin Type	Skin Color	Characteristics
III	Cream white; fair with any eye or hair color; very common	Sometimes mild burn, gradually tans
IV	Brown; typical Mediterranean Caucasian skin	Rarely burns, tans with ease
V	Dark Brown; mid-eastern skin types	Very rarely burns, tans very easily
VI	Black	Never burns, tans very easily

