8.2. Subgroup Analyses

For the safety and efficacy endpoints the following subgroup analyses will be done:

Table 6: Summary of Subgroup Analyses

Subgroup	Specification Values
Age Group 1	$12 - 16 \text{ Years}, 17 - 64 \text{ Years}, \ge 65 \text{ Years}$
Age Group 2	< Median Age, ≥ Median Age
Gender	Male, Female
Race	White, Black or African American, Asian, Other
Ethnicity	Hispanic or Latino, Not Hispanic or Latino
Fitzpatrick Classification Scales	I-IV, V-VI

For the safety analyses, safety will be summarized for all subgroups except Fitzpatrick Classification Scales. For the efficacy analyses, efficacy will be summarized for all subgroups.

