9.2. Local Cutaneous Safety Evaluation

Non-lesional erythema, peeling, dryness, stinging, burning and itching scores will be summarized by treatment group and visit including sample size, frequency count and percentage for each visit. A similar summary will be provided excluding subjects with signs or symptoms present at Baseline.

Non-lesional erythema, peeling, dryness, stinging, burning and itching scores and their corresponding descriptions are listed in Table 7, Table 8, Table 9, Table 10, Table 11 and Table 12 respectively.

Table 7: Scoring of Non-Lesional Erythema

Severity	Score	Description
None	0	No erythema
Mild	1	Light pinkness present
Moderate	2	Definite redness, easily recognized
Severe	3	Intense redness

Table 8: Scoring of Peeling

Severity	Score	Description
None	0	No peeling
Mild	1	Barely perceptible shedding, noticeable only on light scratching or rubbing
Moderate	2	Obvious but not profuse shedding
Severe	3	Heavy scale production

Table 9: Scoring of Dryness

Severity	Score	Description
None	0	No dryness
Mild	1	Slight barely perceptible fine superficial scale
Moderate	2	Clearly perceptible fine scale giving skin a powdery appearance
Severe	3	Marked roughness, cracked skin with fissures

Table 10: Scoring of Stinging

Severity	Score	Description
None	0	No stinging
Mild	1	Slight sharp, tingling/stinging sensation; not really bothersome
Moderate	2	Definite sharp, tingling/stinging sensation; that
		is somewhat bothersome
Severe	3	Sharp, tingling/stinging sensation that has caused definite discomfort

Table 11: Scoring of Burning

Severity	Score	Description
None	0	No burning
Mild	1	Slight warm, burning sensation; not really bothersome
Moderate	2	Definite warm, burning sensation; that is somewhat bothersome
Severe	3	Hot, burning sensation that has caused definite discomfort

Table 12: Scoring of Itching

Severity	Score	Description
None	0	No itching
Mild	1	Slight itching; not really bothersome
Moderate	2	Definite itching that is somewhat bothersome, without loss of sleep
Severe	3	Intense itching that has caused pronounced discomfort; night rest interrupted and excoriation of the skin from scratching may be present

Overall cutaneous tolerance was graded at the Week 12 visit, or the last visit if earlier, using grades shown in Table 13 below.

Table 13: Overall Tolerance

Grade	Score	Description
Excellent	0	No signs of irritation during the study
Good	1	Slight signs of irritation during the study, which resolved by the end of the study

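### Children aged 9–11 enter only the lotion arms, the printed by-treatment tables pool them with everyone else, and the SAP's age bands disagree on whether they are counted

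*SAP*

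**What the plan says.** **Allocation.** SAP 4.1 states the rule for ages 9–11: "They were randomized to DFD-03 group only in a 1:1 ratio of DFD-03 (tazarotene) Lotion 0.1% to Vehicle Lotion". SAP 4.4 gives them a separate randomisation list, "which is independent from the treatment assignment schedule created for ages 12 and older", with four children planned per lotion arm. SAP 4.1 counts these roughly eight children inside the total of about 150. The SAP synopsis waives inclusion criteria 6 and 7 (minimum inflammatory and non-inflammatory lesion counts) for this age group.

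**Comparisons.** The SAP synopsis makes DFD-03 Lotion versus Tazorac Cream, on local tolerability and safety, the primary endpoint. SAP 4.3 extends the aim to "comparability of local tolerability/safety of DFD-03 versus Tazorac Cream and their respective Vehicles".

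**Populations and tables.** SAP 6.5.2 sets no age limit: "All subjects who receive at least one confirmed dose of study product and provide any post baseline safety information will be included". SAP 6.5.3 sets none for ITT either. In SAP 9.2 the local tolerability "scores will be summarized by treatment group and visit including sample size, frequency count and percentage for each visit". TEAEs (SAP 9.3.4) are summarised by treatment and overall, and efficacy (SAP 8.3) is likewise given without an age split. The index printed in SAP 11.2 shows Subgroup as N/A for every table.

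**Age bands.** SAP 7.3 lists "Age Group (12 16 Years, 17 64 Years, 65 Years or Older". SAP 8.2 says "For the safety and efficacy endpoints the following subgroup analyses will be done", and Age Group 1 in its Table 6 uses the same bands, starting at 12. The shell for Table 14.1.3.1 starts its first band at 9 and runs it to 16.

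**The concern.** A child who could be assigned only to a lotion is not a randomised comparator for a cream. Pooled, the DFD-03 column holds the youngest subjects and the Tazorac column holds none, as a result of the design and not of chance. The DFD-03 and Vehicle Lotion columns combine a 2:1 list (age 12 and older) with a 1:1 list (ages 9–11), so children weigh more heavily in the vehicle column. The study is descriptive and plans no stratified or adjusted estimate, so the by-arm columns are themselves the result and nothing downstream corrects them.

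The age bands are a separate defect. As written, Age Group 1 leaves an enrolled cohort out of a planned safety and efficacy subgroup analysis, and the section text and the shell cannot both be programmed. SAP section 2 records that the amendment adding this cohort followed FDA recommendations, yet no printed summary isolates it.

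**Working it through.** **Inputs.** Total about 150, including about 8 children (SAP 4.1). Ratio 2:2:1:1 for age 12 and older, chest/back subjects included, and 1:1 for ages 9–11 (SAP 4.4). Reaction rates of 10–30% for the commonest terms with tazarotene cream 0.1% (Protocol 8). No document gives a rate for ages 9–11 or for vehicle, so those are varied as assumptions.

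**1. The plan's own figures.** 150 × (2, 2, 1, 1)/6 = 50/50/25/25, and 8/2 = 4 per lotion arm. Both match SAP 4.4.

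**2. Share aged 9–11, with the 8 inside the 150.** (150 − 8) × (2, 2, 1, 1)/6 = 47.3/47.3/23.7/23.7. Adding 4/0/4/0:

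| Arm | Expected n | Aged 9–11 | Share |
|---|---|---|---|
| DFD-03 Lotion | 51.3 | 4 | 7.8% |
| Tazorac Cream | 47.3 | 0 | 0% |
| Vehicle Lotion | 27.7 | 4 | 14.5% |
| Vehicle Cream | 23.7 | 0 | 0% |

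If the 8 came on top of 150, the shares would be 4/54 = 7.4% and 4/29 = 13.8%. If they were taken out of the 50 and the 25, they would be 8.0% and 16.0%. With 6 to 10 children inside the 150, the ranges are 5.9–9.7% and 11.1–17.6%.

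**3. Shift in a column from pooling.** Shift = share × (rate at 9–11 − rate at 12+). Let between none and all of the children react:

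- DFD-03: 12+ rate 10%, −0.8 to +7.0 points; 12+ rate 30%, −2.3 to +5.5 points.
- Vehicle Lotion (vehicle rates assumed): 12+ rate 10%, −1.4 to +13.0 points; 12+ rate 30%, −4.3 to +10.1 points.
- Less extreme: if the children's rate is double the 12+ rate, DFD-03 shifts by 0.078 × 10 = 0.8 to 0.078 × 30 = 2.3 points.
- DFD-03 minus Vehicle Lotion: if both arms share one rate within each age group, the true difference is 0, but the pooled columns differ by (0.078 − 0.145) × (rate at 9–11 − rate at 12+), which is −6.0 to +2.0 points.

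**4. Sampling error as a yardstick.** Half-width = 1.96 × √[p(1 − p)(1/n₁ + 1/n₂)], normal approximation. The SAP plans no such interval.

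| Comparison | n₁, n₂ | p = 10% | p = 30% |
|---|---|---|---|
| DFD-03 − Tazorac, all | 51.3, 47.3 | 11.8 | 18.1 |
| DFD-03 − Tazorac, 12+ | 47.3, 47.3 | 12.1 | 18.5 |
| DFD-03 − Vehicle Lotion, all | 51.3, 27.7 | 13.9 | 21.2 |
| DFD-03 − Vehicle Lotion, 12+ | 47.3, 23.7 | 14.8 | 22.6 |

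**5. Age bands side by side.** SAP 7.3 and Table 6 Age Group 1 have 12–16, 17–64 and 65+, so no band holds a 9–11-year-old. Shell 14.1.3.1 has 9–16, 17–64 and 65+, which counts the children but merges them with adolescents. SAP 6.4 fixes the denominator: "Percentages are calculated using the total subjects per treatment group". Under the SAP 7.3 text the rows would therefore total 100 − 7.8 = 92.2% in DFD-03 and 100 − 14.5 = 85.5% in Vehicle Lotion. Under the shell they total 100%.

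**The case against.** The strongest case against runs as follows.

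- **The planned subgroups already yield the 12+ set.** The three Age Group 1 bands together are the 12+ subjects, so for counts (tolerability grades, subjects with TEAEs, IGA success) adding the bands gives the 12+ result and subtraction gives the children. The arithmetic is right. But nobody has planned that display, it does not work for medians of lesion counts or CADI, and the printed index shows no subgroup tables. SAP 11.1 points to a spreadsheet that is not available here, so a split specified there cannot be excluded.
- **The effect is small.** This stands. The extreme shifts need all four children in an arm to react. If 120 of 150 complete, proportionally across arms, the Week 12 half-width for DFD-03 minus Tazorac grows to about 13.2–20.2 points. That limits severity, but it does not make the pooled columns the right ones to compare.
- **Listings show age, and four children per arm support little inference.** Also true: 0 of 4 has an exact 95% upper limit of 60%. A listing is still not a summary, and a descriptive row costs nothing.
- **The rates measure something else.** The 10–30% figures are adverse reactions by term, not visit-level tolerability scores. They serve here only to set a scale.

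Two stronger readings are tempting. A reader might infer that neither comparison involves like-randomised subjects. The documents do not support that: every lotion subject, children included, was randomised between the two lotion arms and only the ratio differs, while all Tazorac and about 92% of DFD-03 subjects come from 2:2:1:1 lists. A reader might also infer that the SAP overlooks these children altogether. It does not: the median split in Age Group 2, the 7-to-12 vital-sign limits in Table 15 and the 9–16 shell band all include them, though none identifies them.

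**Conclusion.** The point holds at moderate weight. By design, children make up about 7.8% of DFD-03 Lotion, 14.5% of Vehicle Lotion and none of the cream arms, and the printed tables pool them. The primary DFD-03 versus Tazorac columns thus include subjects who could not have received cream, and the DFD-03 versus Vehicle Lotion columns differ in age mix. The bias is probably small against a half-width of about 12–18 points, but it can be removed with almost no loss of precision. The age-band contradiction needs no assumption about rates and has to be reconciled in any case.

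The shares assume 8 children inside about 150, split 4 and 4. The shifts assume the stated ranges of reaction rates. The statement that no table separates the children rests on the printed SAP text, index and shells.

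**What to change.** 1. **Bands.** Use 9–11, 12–16, 17–64 and 65+ in SAP 7.3, in Table 6 Age Group 1 and in shell 14.1.3.1. Mark the cream columns of the 9–11 row 'not applicable by design'. That row is then the descriptive summary of the cohort.

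2. **A 12-and-older display.** Keep all population definitions and all all-subjects tables. In SAP 9.2, 9.3 and 8.3 add a four-arm display restricted to age 12 and older, to be used to describe DFD-03 versus Tazorac and each active versus its own vehicle. It should cover:
   - local tolerability, Tables 14.2.2.2.1 to 14.2.2.2.6;
   - the TEAE overview (14.3.1.1) and the SOC/PT table (14.3.1.2);
   - Week 12 ITT efficacy, Tables 14.2.1.1.3.1, 14.2.1.2.3.1, 14.2.1.3.3 and 14.2.1.4.3.

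   State that 14.2.1.1.3.1 and 14.2.1.2.3.1 draw on the same imputed data sets as their all-subjects versions. State that percent change (14.2.1.3.3) and CADI (14.2.1.4.3) follow the data handling of their all-subjects tables, with no multiple imputation implied.

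**Cost.** 6 + 2 + 4 = 12 extra tables, and about four fewer subjects in each lotion arm of those displays. At 10–30% rates the half-width goes from 11.8–18.1 to 12.1–18.5 points for DFD-03 minus Tazorac, and from 13.9–21.2 to 14.8–22.6 for DFD-03 minus Vehicle Lotion. If the plan is already final, SAP section 2 provides for departures from it to be noted in the study report.
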